5.3 Other Outcomes of Interest

None.

5.4 Safety Outcomes

To analyse local and systemic reactions after ILIT and SCIT (assessed by clinician during on site monitoring 60 min after the intervention and by study participant at home for the next two days).

6. STUDY DESIGN

6.1 General study design and justification of design

This is a prospective, comparative, clinical open label pilot study. From patients with grass pollen allergy who undergo a pre-seasonal SCIT scheme with Polvac™ Grass+RyeSCIT at the USZ Allergy Unit, 30 patients will be recruited for the study that is illustrated in Figure 2.

Four to six weeks after end of SCIT treatment (at maximal maintenance dose), the patients will be randomized to one out of two treatment groups and receive one additional allergen injection. Fifteen patients will be allocated to receive another subcutaneous injection with 0.5 ml (2000 U) Polvac™

Grass+Rye. The other 15 patients will be allocated to receive an intralymphatic injection of 0.1 ml Polvac™ Grass+Rye with 400 U allergen. Both SCIT and ILIT injections are performed by ultrasound-guidance as to assure injection into the lymph node (ILIT) or 1 cm next to the lymph node (SCIT).

The FNA of lymph node tissue will be conducted at 2, 6 or 24 hours after allergen injection. At the same time, FNA of a contralateral lymph nodes will be performed as baseline. Venous blood will be sampled at all visits: at baseline as well as after 2, 6 or 24 hours, after 7 days and after 28 days of the allergen ILIT or SCIT. The FNA is performed by ultrasound-guidance.

[figure not shown]

Figure 2. Study design illustrated schematically the open-label clinical pilot study for assessment of immunological and inflammatory responses to a single ILIT or SCIT in patients receiving grass pollen immunotherapy with Polvac™ Grass+Rye.

6.2 Methods of minimising bias

6.2.1 Randomisation

All patients who give consent for participation and who fulfil the inclusion criteria will be randomized to either SCIT or ILIT treatment group with a 1:1 allocation. The randomisation list will be computer-generated by a statistician using a permuted block design (groups of six). Before trial initiation, randomisation envelopes will be given to the study physician who will then be responsible of envelope storage and appropriate use. Allocation concealment will be ensured as the randomisation envelopes will not be opened before the patient has been recruited into the trial, which takes place after screening has been completed.

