Objective(s):	The study seeks primarily to determine hallmarks in immunological responses (analysis of inflammatory cell and proteins) in lymph nodes and in peripheral blood after allergen ILIT and SCIT.
Outcome(s):	
 1) Fine needle aspiration (FNA) material of lymph node tissue at baseline and 2 or 6 or 24 hours after allergen ILIT or SCIT will be evaluated for changes in cell populations and cell functions. 2) Immunological changes (analysis of cell populations and functions ex vivo and in vitro) in peripheral blood at baseline, after 2 or 6 or 24 hours, after 7 days and after 28 days of allergen ILIT or SCIT.

Study design:	
This is a prospective, comparative, clinical study. We will recruit 30 grass-pollen allergic patients undergoing pre-seasonal short-term SCIT scheme with Polvac™ Grass+Rye at the USZ Allergy Unit. 4 weeks after last SCIT injection and after reaching maintenance SCIT dose (2000 U), the patients will receive an additional allergen injection as part of the study. Patients will be randomized into the 3 different groups with 10 participants per group. Patients will receive a single ultrasound-guided injection with Polvac™ Grass+Rye ILIT (0.1 ml, 400 U) or SCIT (0.5 ml, 2000 U).
 
FNA of lymph node tissue will be conducted at baseline and at 2, 6 or 24 hours after allergen injection. Venous blood will be sampled at baseline, after 2, 6 or 24 hours, after 7 days, and after 28 days of allergen injection.

Inclusion / Exclusion criteria:	
Included are patients between 18 and 55 years of age with grass-pollen allergy and undergoing pre-seasonal short-term-scheme Polvac™ Grass+Rye SCIT at the USZ Allergy Unit for treatment of allergic rhinoconjunctivitis.
 
Exclusion criteria are significant allergy to house dust mite or pet animal allergens, uncontrolled asthma, upper airway disease, severe pulmonary disease, recent allergic reactions, immunosuppression, cardiovascular disease, malignant disease, conspicuous lymph node size or morphology, use of ACE-blockers and any other diseases or conditions rendering the treatment of anaphylactic reactions difficult.

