Measurements and procedures:	
A single injection of grass pollen allergen extract (Polvac™ Grass+Rye) will be administered by ILIT or SCIT. FNA of material from lymph node tissue will be aspirated 6 hours after allergen injection. Opposite inguinal lymph node tissue will be aspirated by FNA as a baseline comparison. Venous blood will be sampled at baseline, after 2, 6 or 24 hours, after 7 days, and after 28 days of allergen injection. For safety reasons, as to exclude respiratory cases, peak flow measurement will be performed before treatment and 40 minutes after treatment.

Study Product / Intervention:	
A single dose of grass pollen allergen extract (Polvac™ Grass+Rye from Bencard AG, Switzerland) will be injected via ultrasound-guided ILIT or SCIT route. Different doses will be injected according to the 2 study arms: (i) ILIT 0.1 ml, 400 U or SCIT 0.5 ml, 2000 U.

Control Intervention:	No control intervention is planned.
Number of Participants with Rationale:	For this pilot, unblinded study with three treatment groups, no sample size calculation is made. We assume that 10 patients per treatment group will enable us to describe immunological features of the three treatments.
Study Duration:	01.09.2023 to 31.12.2024
Study Schedule:	Plan: October 2023 First-Participant-In; March 2024 Last-Participant-Out.
Investigators:	
[name], Department of Dermatology, University of Zurich, [name], Switzerland
 
[name], MD, Department of Dermatology, University of Zurich, [name], Switzerland
 
[name], USZ Allergy Unit, [name], Switzerland

Study Centre(s):	Department of Dermatology, University Hospital Zurich, Zurich
Statistical Considerations:	All data are analysed and reported with descriptive statistics.
GCP Statement:	This study will be conducted in compliance with the protocol, the current version of the Declaration of Helsinki, ICH-GCP, as well as all national legal and regulatory requirements.

ABBREVIATIONS

AE	Adverse Event
ASR	Annual Safety Report
ARC	Allergic Rhinoconjunctivitis
BASEC	Business Administration System for Ethical Committees, (https://submissions.swisstethics.ch/en/)
CA	Competent Authority (e.g. Swissmedic)
CRF	Case Report Form
ClinO	Ordinance on Clinical Trials in Human Research (in German: KlinV, in French: OClin, in Italian: OSRUM)
eCRF	Electronic Case Report Form
CTCAE	Common terminology criteria for adverse events

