DSUR	Development safety update report
FNA	Fine needle aspiration
GCP	Good clinical practice
IB	Investigator's Brochure
Ho	Null hypothesis
HRA	Federal Act on Research involving Human Beings (in German: HFG, in French: LRH, in Italian: LRUM)
IEC	Independent Ethics Committee
IMP	Investigational Medicinal Product
IIT	Investigator-initiated Trial
ILIT	Intralymphatic immunotherapy
ITT	Intention to treat
PI	Principal Investigator
SCIT	Subcutaneous Immunotherapy
SDV	Source Data Verification
SmPc	Summary of Product Characteristics
SOP	Standard Operating Procedure
SPC	Summary of product characteristics
SUSAR	Suspected Unexpected Serious Adverse Reaction
TMF	Trial Master File
USZ	University Hospital Zurich

STUDY SCHEDULE

Table 1. Illustrating the study schedule with all interventions divided into the five visits. Patients will receive 6 SCIT injections as standard of care (not part of the study). 4-6 weeks later, the patients will be included in the clinical trials for assessment of immunological characteristics after a single ILIT or SCIT with subsequent fine needle aspiration (FNA), adverse event (AE) monitoring, and venous blood collection.

Visit / time point	1 Screening < 6 weeks of last SCIT	2 AIT	3 FNA	4 Follow-up	5 Follow up
		Day 0	Day 0-1	Day 7	Day 28
Required personnel	Nurse/MD	MD	MD	Nurse/MD	Nurse/MD
Informed consent	x				
Randomization	x				
Medical history	x				
Physical exam	x				
Incl./excl. criteria	x				
Blood samples		x	x	x	x
Pregnancy test		x			
AEs/Concomitant medication		x			x
Peakflow measurement		x*			
Injection: Study drug administration		x			
FNA (2x)			x**		
AE monitoring (1h observation at allergy unit after injection)		x			
Dispensing rescue medication		x			

* Peakflow measurement will be performed immediately before injection and 40 minutes after injection

** The FNA is performed 2, 6 or 24 hours after the Polvac™ ILIT or SCIT, and the injected (ILIT) or draining (SCIT) lymph node is used for FNA. For baseline reference, a contralateral lymph node is also aspirated.

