5. STUDY OUTCOMES

5.1 Primary Outcome

The FNA material of lymph node tissue at baseline and 2, 6 or 24 hours after allergen injection (via ILIT or SCIT) will be evaluated for changes in cellular composition and functions.

Immunological changes in peripheral blood at baseline, after 2, 6 or 24 hours, after 7 days and after 28 days of allergen ILIT or SCIT will be analysed by measuring cellular composition and functions in whole blood and in culture blood cells as well as inflammatory proteins and antibodies in serum.

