9.2 Assessments of outcomes

9.2.1 Assessment of primary outcome

FNA material of lymph node tissue at baseline and 6 hours after allergen injection (via ILIT or SCIT) will be evaluated for changes in lymph node cell populations and cell culture expression patterns.

Immunological changes (analysis of cell populations and cell cultures) in peripheral blood at baseline, after 2, 6 and 24 hours and at 7 and 28 days after allergen injection (via ILIT or SCIT).

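### The protocol contradicts itself on when the early samples are taken and, if several hours are used, does not say how the hour is allocated or analysed

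*Combined protocol and SAP*

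**What the plan says.** **Aspiration time.** The Synopsis (Measurements and procedures) states "FNA of material from lymph node tissue will be aspirated 6 hours after allergen injection", and 9.2.1 agrees: "FNA material of lymph node tissue at baseline and 6 hours after allergen injection (via ILIT or SCIT". The Synopsis design row instead states "FNA of lymph node tissue will be conducted at baseline and at 2, 6 or 24 hours after allergen injection", and 6.1 states "The FNA of lymph node tissue will be conducted at 2, 6 or 24 hours after allergen injection". The Synopsis outcomes row, the Table 1 footnote, 5.1, 8.2.1, 9.3.2 and 9.3.3 also give three alternative hours. Sections 5.1 and 9.2.1 therefore describe the same primary outcome differently.

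**Early blood.** Section 9.2.1 gives blood "after 2, 6 and 24 hours and at 7 and 28 days after allergen injection", in addition to baseline. Section 8.2.1.3 has a single early draw at one of the three hours, and 8.7 counts four blood collections and two aspirations per patient.

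**Visit lists.** Sections 9.3.2 and 9.3.3 list the same pair of aspirations and the same early draw under both Visit 2 and Visit 3. The Visit 3 draw is labelled as preceding the injection. Section 10.1.2.4 places everything except the day 28 draw on the day of the pregnancy test.

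**Allocation and analysis.** Section 6.2.1 randomises route in permuted blocks of six: patients "will be randomized to either SCIT or ILIT treatment group with a 1:1 allocation". Sections 6.2.3 and 7.3 also speak of two treatment groups only. Section 11.4 compares SCIT with ILIT by ANOVA or Kruskal-Wallis and names no hour factor or stratum.

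**Group count.** The Synopsis has three groups of 10; 3.5, 6.1, 7.3 and 8.1 have two groups of 15.

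**The concern.** Site staff cannot tell from the text when a given participant is to be aspirated, or how many early draws are due. That needs no statistical assumption.

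If three hours are used, time since injection becomes a source of variation in the aspirate and the early draw. Left out of the analysis, it inflates the error of the route comparison. If the arms have different mixes of hours, it also biases that comparison. The study is open label, so an hour fixed after the route is known could follow the route. The contralateral node does not solve this: 6.1 has it aspirated at the same time as the treated node, so subtracting it leaves the treated node's time course in the result. Blood at day 7 and day 28 is not affected.

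Comparing the two routes is the primary objective (4.2), and 3.1 wants the results to guide the timing and dosing of larger studies. The sampling hour therefore matters to the study's own purpose.

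**Working it through.** **Counts from the documents.** There is no power calculation to reproduce (11.2).
- Arms: 30 / 2 = 15. Blocks: 30 / 6 = 5. Route-by-hour cells with two arms: 15 / 3 = 5 patients.
- Blood draws with one early draw: 1 + 1 + 2 = 4, which agrees with 8.7. With three early draws (9.2.1): 1 + 3 + 2 = 6, which does not.
- Section 10.1.2.4 fits neither a 24 h sample nor the day 7 draw.
- Visits 2 and 3 added together would give five draws and four aspirations. Table 1 has the aspirations at Visit 3 only, 8.4 places aspiration and early blood at the third visit, and 8.7 counts two and four. The second listing is therefore a duplicate.

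**Assumptions for the size (none is in the documents).** Within-hour SD 1; hour effects of −h, 0 and +h SD; mean route difference 1 SD; 15 per arm; two-sided 5% test. Simulated figures are good to about one percentage point.

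**Cost of the hour term with five per cell.** Noncentrality = 1 / √(2/15) = 2.74. Without an hour effect, power is 0.753 on 28 df and 0.751 on 26 df.

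**Error inflation if hour is ignored.** With 5/5/5 in each arm, hour adds 10h² to each arm's sum of squares. The expected error variance is (28 + 20h²) / 28, which is 1.71 at h = 1. With balanced hours and no route effect, the test without the term then rejects in only about 1% of trials.

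**Bias from an unequal mix.** With 7/5/3 against 3/5/7, the arm means shift by (−7 + 3)/15 = −4/15 and (−3 + 7)/15 = +4/15 steps. The bias is 8/15 = 0.53h, that is 0.27 SD at h = 0.5 and 0.53 SD at h = 1. Simulated false-positive rates are about 8% and 14%; with the hour term they are about 5%. At 6/5/4 against 4/5/6 the bias is 4/15 = 0.27h and the rate stays below 5%.

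**Hours drawn at random.** The average false-positive rate is 5% with or without the term. An imbalance at least as large as 7/5/3 against 3/5/7 has probability 9%. The chance of 5/5/5 in both arms is [15! / (5!³ × 3¹⁵)]² = 0.0527² = 0.3%.

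**Power, ANOVA without → with the hour term.**

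| Hour effect | Balanced cells | Random hours |
|---|---|---|
| None | 75% → 75% | 75% → 72% |
| 1 SD per step, equal in both arms | 53% → 75% | 53% → 72% |
| 1 SD per step, one arm only | 63% → 68% | 63% → 65% |
| 1 SD per step, opposite | 54% → 52% | 53% → 49% |

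**Rank tests, random hours, unstratified → stratified by hour (van Elteren).** No hour effect: 73% → 67%. Equal effect of 0.5 SD per step: 66% → 66%. Equal effect of 1 SD per step: 51% → 67%.

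**Within one hour, 5 v 5 (8 df).** Power is 29% for 1 SD; 80% power needs 2.02 SD.

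**The case against.** The strongest case against this is that the study is a descriptive pilot. It has no single primary endpoint (4.2), no hypothesis of a given difference (11.1) and no sample size calculation (11.2), so power and error rates measure targets the plan does not set. That stands as a limit on what is at stake. It does not excuse contradictory sampling times, and 11.4 does plan group tests.

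Four stronger readings are tempting, and the documents do not support them.
- A reader might infer that five draws and four aspirations are planned. Table 1, 8.4 and 8.7 contradict this.
- A reader might infer that 11.4 rules out adjustment for hour. It only fails to name it: ANOVA could carry a second factor, although Kruskal-Wallis as written could not.
- A reader might infer that the route comparison is already confounded or its error rate inflated. No text says that the hour is chosen after the route, and random hours leave the average rate at 5%.
- A reader might infer that adding hour to the model always recovers the lost power. The large gain needs an hour effect equal in both arms. The quantitative theory in 4.1, that only part of the SCIT allergen reaches the node, gives a reason why the time course may differ by route.

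Figures 2 and 4 were not available to me and may show how hours are assigned. Blocks of six would suit two routes by three hours, but they suit three groups equally well, so block size settles nothing. Nor can the Synopsis's three groups be taken to be the three hours, because its sample size rationale calls them treatments.

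**Conclusion.** The contradiction on sampling times is a matter of text and holds without assumptions. The gaps in allocation and analysis hold for the available text, and only if more than one hour is kept for a sample type.

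Their size depends on assumed hour effects, since the documents give none. The main risk is bias from an unequal mix of hours: about half an SD under the assumed 7/5/3 split at 1 SD per step. Setting the hour on the concealed list, in balance, is the main protection. The hour term is secondary: with balanced cells it costs almost nothing if hour has no effect, gains from about 5 to 22 points if the effect is 1 SD per step in one or both arms, and can lose about 2 points if the effects are opposite. The consequence is for precision and interpretation of the aspirate and early-blood comparisons, not for a confirmatory conclusion. It should be settled before the first patient enters, because sampling hours cannot be changed afterwards.

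**What to change.** 1. The sponsor reconciles sampling times and draw counts across the Synopsis, Table 1, 5.1, 6.1, 8.2.1, 8.2.1.3, 8.7, 9.2.1, 9.3.2, 9.3.3 and 10.1.2.4, removes the duplicate listing and corrects the Visit 3 label. The Synopsis's three groups of 10 must be reconciled with the body's two groups of 15, because this sets the number per hour.
2. If more than one hour is kept, 6.2.1 states that the concealed list sets hour together with route, and that each block of six contains every route-by-hour combination once (5 per cell with two arms of 15). This is the main fix.
3. Section 11.4 then presents aspirate and early-blood results descriptively by route and hour, and includes hour as a factor in the ANOVA. A van Elteren test is optional for ranked data. The text should say that the route term is an average over hours, and that 5 v 5 within an hour can detect only about 2 SD. Day 7 and day 28 blood keep the planned tests.

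If a single hour is chosen for a sample type, steps 2 and 3 fall away for it.

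**Cost.** Wording in about ten places and a regenerated list; no extra patients, visits or samples. Scheduling becomes less flexible because the list fixes the hour, and replacements under 7.4 may leave the cells slightly uneven. The hour term uses two degrees of freedom. If hours were left random and hour had no effect, the loss would be about 3 points of power for ANOVA and about 6 for van Elteren. That is why balancing belongs in the main fix and the stratified rank test stays optional.

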6.2.2 Blinding procedures

Not applicable. The study is not blinded.

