7.2 Recruitment and screening

We will recruit 30 patients directly at the USZ Allergy Unit. All 30 participants must have a type-1-sensitisation to grass pollen allergens and be undergoing pre-seasonal short-term SCIT scheme with Polvac™ at the USZ Allergy Unit in winter 2023/2024.

Patients will be invited to a screening visit 1 to 60 days before the intervention, where an extensive interview will be conducted and the informed consent will be signed by the patient and the medical investigator. The informed consent will be uploaded to the clinical information system (KISIM) and filed

into the trial master file (TMF). At the screening visit there will be a medical interview assessing all inclusion and exclusion criteria and a short clinical exam (auscultation of the lungs and the heart, blood pressure measurement).

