7.3 Assignment to study groups

The 30 patients will be randomized to the two different equally-sized treatment groups (ILIT 400 U and SCIT 2000 U), with each 15 patients per group.

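### A single stated block size of six in an open-label, single-unit trial lets anyone who tracks allocations know on average a quarter of them in advance; one 15:15 list, held outside the recruiting team, would reduce this

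*Combined protocol and SAP*

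**What the plan says.** Section 6.2.1 states that patients "will be randomized to either SCIT or ILIT treatment group with a 1:1 allocation" and that the list is "computer-generated by a statistician using a permuted block design (groups of six". It gives no second block size and no strata. Before the trial starts, "randomisation envelopes will be given to the study physician who will then be responsible of envelope storage and appropriate use". The stated safeguard is that "randomisation envelopes will not be opened before the patient has been recruited into the trial, which takes place after screening has been completed".

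On blinding, section 6.2.2 says: "Not applicable. The study is not blinded". Section 7.2 says: "We will recruit 30 patients directly at the USZ Allergy Unit". Section 7.3 sets two equal groups, "with each 15 patients per group". The synopsis conflicts with this: "Patients will be randomized into the 3 different groups with 10 participants per group". Sections 6.1, 6.2.1, 7.3 and 8.1 all describe two groups, so the two-group design is used here and the synopsis version is a sensitivity check.

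Section 12.1.1 adds that, because the trial is open label, the randomisation list is accessible to any physician. It does not say whether that covers allocations not yet used.

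**The concern.** Concealment has two parts: nobody opens an envelope early, and nobody can work out what is in it. Section 6.2.1 deals with the first. With a known block of six at 1:1, the second fails once three patients of a block have gone to one arm, because the rest of that block must go to the other. In an unblinded trial at one unit, the staff can see every earlier allocation.

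A person who knows or suspects the next arm can influence who is enrolled next, or when. The protocol leaves some room for this. Section 7.1 leaves the comorbidity exclusions to the recruiting physician's judgement, section 7.2 allows screening from 1 to 60 days before the intervention, and section 7.4 allows discretionary exclusion and replacement. The primary objective in section 4.2 is a comparison of ILIT with SCIT, and section 11.4 plans group tests. Apart from randomisation, section 6.2.3 offers only an age range and neutral recruitment as protection.

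**Working it through.** The plan gives no predictability figure, so there is none to reproduce.

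**Inputs.** Block of six and 1:1 ratio (6.2.1), so 3 ILIT and 3 SCIT per block; 30 patients, 15 per arm (7.2, 7.3); open label (6.2.2); one unit (7.2). Consistency check: 30/6 = 5 complete blocks, and 5 × 3 = 15 per arm, as stated.

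**Known for certain.** A 3:3 block has C(6,3) = 20 equally likely orders. In 12 of them only the last allocation is fixed by those before it, in 6 the last two, in 2 the last three.

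- Mean per block: (12×1 + 6×2 + 2×3)/20 = 30/20 = 1.5 of 6 = 25%. The closed form 2m/(m+1) with m = 3 also gives 1.5.
- Over five blocks: 5 × 1.5 = 7.5 of 30. The minimum is 5 and the maximum 15; the probability of 10 or fewer is 0.97.

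**Guessed correctly.** The rule is to guess the arm with more places left in the block. The chance of being right at positions 1 to 6 is 0.5, 0.6, 0.6, 0.7, 0.7 and 1.0, which sums to 4.1 of 6 = 68%. The closed form m + 2^(2m−1)/C(2m,m) − 1/2 gives 3 + 32/20 − 0.5 = 4.1. Over five blocks this is 20.5 of 30, against 15 by chance.

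**One 15:15 list over exactly 30 positions** (m = 15).

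- Certain: 30/16 = 1.9.
- Guessed correctly: 15 + 2^29/C(30,15) − 0.5 = 15 + 536,870,912/155,117,520 − 0.5 = 18.0.

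**Randomly varied block sizes.** The sizes are assumptions, not in the documents. The figures come from simulating 20,000 lists of 30, with a guesser who knows the possible sizes but not their order.

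| List | Known for certain | Guessed correctly |
|---|---|---|
| Fixed blocks of six | 25% (7.5 of 30) | 68% (20.5 of 30) |
| One 15:15 list | 6% (1.9 of 30) | 60% (18.0 of 30) |
| Random blocks of 4 and 6 | 5.7% | 68.8% |
| Random blocks of 2, 4 and 6 | 3.8% | 69.9% |

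Varying the size removes most of the certainty but none of the guessing.

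**Sensitivity to the synopsis.** With three groups, a block of six is 2:2:2. Of its 90 orders, 72 fix one allocation and 18 fix two: (72 + 36)/90 = 1.2 of 6 = 20%.

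**Price of one list if recruitment stops at 20.** The arm split is hypergeometric.

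- P(10:10) = C(15,10)²/C(30,20) = 3003²/30,045,015 = 0.300.
- P(11:9 either way) = 2 × 1365 × 5005/30,045,015 = 0.455.
- P(difference of 4 or more) = 1 − 0.755 = 0.245, about 25%.

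With blocks of six, 20 patients are three full blocks plus two patients, so the difference is at most 2.

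**The case against.** The strongest reply is that predictability is not bias. A reader might infer from the 25% that enrolment will be steered or that the comparison is compromised; the documents do not support that. If a recruiter shifted patients g standard deviations up when guessing one arm and down when guessing the other, the expected arm difference would be 2 × (2×20.5 − 30)/30 × g = 0.73g, against 0.39g with one list. The documents give no value for g and no sign that it differs from zero. Nor do they say that the envelope-holding physician chooses the patients: sections 7.2 and 9.3.1 assign screening to the medical investigator, and section 14.2.1 assigns screening and recruitment to the Allergy Unit team. The 4-6 week window after the last SCIT injection limits how far patients can be reordered. Each patient also has a baseline node and blood sample, which limits the effect of baseline imbalance, though not of differences in responsiveness. All of this stands, and it limits the claim to an avoidable weakness.

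A second reply is that this is a descriptive pilot with no hypothesis to confirm (11.1) and no single primary endpoint (4.2). That lowers the stakes but does not remove them, since the comparison is the stated objective and tests between the arms are planned.

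A third is that section 12.1.1 makes block size irrelevant. If its access rule covers unused allocations, all of them can be looked up, and a new list would be just as readable. The text does not settle whether it does, so one cannot conclude that every allocation is already exposed. It does follow that changing the list without restricting access would not be enough.

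Finally, blocks keep the arms balanced over time and if recruitment stops early, which section 2.9 allows. That is a real cost of giving them up.

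**Conclusion.** The point holds as a modest, inexpensive improvement to concealment. The expected share of allocations known for certain is 25% (7.5 of 30, range 5 to 15), and 68% can be guessed correctly against 50% by chance. These figures describe a person who knows the block size, follows every allocation and knows where each block starts; an open-label, single-unit trial makes that possible. They assume six is the only block size and that there are no strata, since none are mentioned. Under the synopsis's three groups the certain share would be 20%. The closed-envelope rule does not change any of these figures. No steering is shown, and the size of any resulting bias cannot be derived from the documents.

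**What to change.** Before the first patient is randomised:

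1. Replace the blocks with one random 15:15 list over the 30 positions, plus spare positions for the replacements that section 7.4 allows. The 1.9 and 18.0 figures are for exactly 30 positions; spares change them slightly.
2. Take the restriction details out of the site protocol and keep them with the statistician.
3. Have the pharma team, which already provides and logs each dose (8.1.1, 8.8), hold the envelopes and release each one only after eligibility is confirmed.
4. In the same amendment, limit the list access in section 12.1.1 to allocations already made.
5. Reconcile the synopsis with section 7.3 on the number of groups, since the list depends on it.

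If blocks are kept for balance, randomly varied sizes are the weaker alternative: about 4-6% certain, but still about 69-70% guessed correctly.

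The cost is a new list and short edits to sections 6.2.1 and 12.1.1, with no extra staff. The statistical price is possible imbalance on early stopping: at 20 patients, about a 25% chance of a difference of 4 or more, against at most 2 with blocks of six.
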